11.3.1.1. Study Phases for Concomitant Medication

| Study Phase | Definition |
|-------------|--|
| Prior | If medication end date is not missing and is before 28 days prior to screening visit |
| Concomitant | Any medication that is not a prior |

NOTES:

 Please refer to Appendix 6: Reporting Standards for Missing Data for handling of missing and partial dates for concomitant medication. Use the rules in this table if concomitant medication date is completely missing.

11.3.2. Treatment States for Adverse Events Data

| Treatment State | Definition |
|-----------------|--|
| Pre-Treatment | AE Start Date < Study Treatment Start Date if AE start time not available; else |
| Pre-mealment | AE Start Date time < Study Treatment Start Date time |
| On-Treatment | If AE onset date is on or after treatment start date & on or before treatment stop date. |
| | Study Treatment Start Date ≤ AE Start Date ≤ Study Treatment Stop Date |
| Post-Treatment | If AE onset date is after the treatment stop date. |
| | AE Start Date > Study Treatment Stop Date |
| Onset Time | If Treatment Start Date > AE Onset Date = AE Onset Date - Treatment Start Date |
| Since 1st Dose | If Treatment Start Date ≤ AE Onset Date = AE Onset Date - Treatment Start Date +1 |
| (Days) | Missing otherwise. |
| Duration (Days) | AE Resolution Date – AE Onset Date + 1 |
| Drug-related | If relationship is marked 'YES' on CRF OR value is missing. |

NOTES:

• If the study treatment stop date is missing then the AE will be considered to be On-Treatment.

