7.2. Adverse Events Analyses

Adverse Events will be coded using Medical Dictionary for Regulatory Activities (MedDRA) central coding dictionary, Version 21.0.

See Appendix 3: Study Phases and Treatment Emergent Adverse Events to determine treatment states for AE data. Handling of partial dates for AEs is outlined in Appendix 6: Reporting Standards for Missing Data. In the rare case when it is not possible to assess treatment emergence, the AE will be classified as treatment emergent (i.e. the worst case).

AE Severity is classified as mild (grade = 1), moderate (grade = 2), or severe (grade = 3). AEs with a missing severity will be classified as severe. If a participant reports an AE more than once within that SOC (System Organ Class)/ PT (Preferred Term), the AE with the worst case severity will be used in the corresponding severity summaries.

Relationship to study treatment, as indicated by the Investigator, is classified as "not related" or "related". AEs with a missing relationship to study medication will be regarded as "related" to study medication.

All AE tabulations will be performed separately for Part 1 and Part 2, by dose, and will include the number and percentage of participants. For each study part and cohort, incidence of AEs will be tabulated by the following:

- All AEs by SOC and PT
- All related AEs by SOC and PT
- All AEs by SOC, PT and Severity
- All related AEs by SOC, PT and Severity

All AEs leading to permanent discontinuation of study treatment will be identified by using the variable pertaining to outcome on the Adverse Events page of the CRF, and listed separately for each study part and cohort.

Serious adverse events (SAEs) are those events recorded as "Serious" on the Adverse Events page of the CRF, and will be listed separately for each study part.

The details of the planned displays are provided in Appendix 11: List of Data Displays.

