11.3. Appendix 3: Study Phases and Treatment Emergent Adverse Events

11.3.1. Study Phases

Assessments and events will be classified according to the time of occurrence relative to dosing.

| Study Phase | Definition |
|----------------|---|
| Pre-Treatment | Date ≤ Study Treatment Start Date |
| On-Treatment | Study Treatment Start Date < Date ≤ Study Treatment Stop Date |
| Post-Treatment | Date > Study Treatment Stop Date |

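### An adverse event timed before the first dose on Day 1 meets both the Pre-Treatment and the On-Treatment definition, so it can enter the treatment-emergent counts

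*SAP*

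**What the plan says.** SAP section 7.2 takes its classification from the appendix: "See Appendix 3: Study Phases and Treatment Emergent Adverse Events to determine treatment states for AE data". Within that appendix, section 11.3.2 gives three states.

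- **Pre-Treatment** has two branches. Without a start time it goes by date: "AE Start Date < Study Treatment Start Date if AE start time not available; else". With one, it goes by date and time: "AE Start Date time < Study Treatment Start Date time".
- **On-Treatment** has one branch, by date, stated in words ("If AE onset date is on or after treatment start date & on or before treatment stop date") and as a formula ("Study Treatment Start Date ≤ AE Start Date ≤ Study Treatment Stop Date").
- **Post-Treatment** covers any onset date after the stop date.

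Two other passages bear on Day 1. Section 7.2 has a fallback: "In the rare case when it is not possible to assess treatment emergence, the AE will be classified as treatment emergent (i.e. the worst case". Section 11.3.1 has a general phase table, introduced by "Assessments and events will be classified according to the time of occurrence relative to dosing", in which Pre-Treatment is "Date ≤ Study Treatment Start Date".

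**The concern.** The two rows use different clocks. One splits Day 1 at the moment of dosing and the other takes the whole of Day 1, so they overlap on the pre-dose hours. Two programmers who both follow the SAP could produce different adverse event tables.

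This matters for three reasons. Adverse events are part of the primary safety endpoint (section 2.2). The treatment-emergent summaries for dosed participants (Tables 3.1, 3.2, 3.7 and 3.8) depend on this classification. The hours before the first dose are also not empty: the single-dose schedule in Appendix 2 places spirometry, the start of telemetry, ECG and vital signs, and a blood draw before dosing, and allows inhaler training to be moved to Day 1. An event provoked by one of these procedures could be reported as treatment-emergent.

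**Working it through.** There is no planned figure to reproduce, so the check applies the rows literally to test onset times.

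**Assumptions, for illustration only:** first dose on Day 1 at 09:00, last dose on Day 14. The SAP gives no clock time for dosing.

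| Onset | 11.3.2 as written | 11.3.1 phase table | 11.3.2 with the fix below |
|---|---|---|---|
| Day -1, 20:00 | Pre | Pre | Pre |
| Day 1, 07:00 | **Pre and On** | Pre | Pre |
| Day 1, no time recorded | On | Pre | On |
| Day 1, 09:00 | On | Pre | On |
| Day 1, 11:00 | On | Pre | On |
| Day 2, 07:00 | On | On | On |
| Day 14, 23:00 | On | On | On |
| Day 15, 07:00 | Post | Post | Post |

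Only the Day 1 event with a recorded pre-dose time falls into two states. This does not depend on the assumed hour of dosing.

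**Does anything else in the SAP resolve it?**

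- The closing word of the first Pre-Treatment branch chooses between date and date-time inside that row. It does not rank that row above the On-Treatment row.
- The section 7.2 fallback is for events whose emergence cannot be assessed. An event with a known pre-dose time can be assessed.
- The partial-date rule in section 11.6.2.1 deals with a missing day, not with a known time.
- Section 11.3.1 refers to events as well as assessments, but it sets the opposite boundary: every Day 1 event, including one two hours after dosing, is Pre-Treatment. It adds a second conflict.

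**Weight of one event.** The Part 1 mock shells (SAFE_T1, SAFE_T4, SAFE_T5) use columns of 4, 6 and 12 participants. Those sizes are taken here as an assumption. One participant moves an incidence by 100/N percentage points:

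- 100/4 = 25.0
- 100/6 = 16.7
- 100/12 = 8.3

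**The case against.** The best defence is that the intent is clear. The date-time branch in the Pre-Treatment row serves only to settle events on the day of first dosing. Read from the top down, or with the specific rule over the general one, a timed pre-dose event is Pre-Treatment and nothing is miscounted. That is a sensible reading, and it rules out the claim, which a reader might infer, that pre-dose events will be counted as on-treatment or will appear twice. But the SAP does not state that order, and the On-Treatment row applied as written gives the other answer. The defence shows what was probably meant, not what is specified.

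The second defence is that such events may be few. The screening and follow-up schedule lists SAE review at screening but AE review only at follow-up, so collection of non-serious events may begin close to dosing. The schedules by day are too broken in the available text to settle when it starts. This stands as a limit on size.

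Third, the effect is contained. Relatedness is assigned by the investigator, all adverse events are listed, the serious-event and discontinuation tables are not titled treatment-emergent, the same rule applies to placebo, and the error can only over-count. All of this is fair. It means no event is hidden, but the treatment-emergent tables remain ambiguous.

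A reader might also infer that about a third of the on-treatment window in the single-dose COPD cohort is pre-dose, from 8.5/24 = 35% with dosing at 08:30. The documents do not support using that figure. It is a share of clock hours, not of events, it rests on an assumed dosing time, and it needs an on-treatment window of one calendar date, which is a matter of the stop-date cut-off. Over 14 days the same hours are 8.5/336 = 2.5%.

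**Conclusion.** The point holds in limited form. In SAP section 11.3.2 an adverse event with a recorded start time before the first dose on Day 1 satisfies two states, no precedence is given, and such an event can therefore enter the treatment-emergent counts. Without a recorded time there is no overlap within 11.3.2: a Day 1 event is On-Treatment only.

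The number of affected events cannot be known from the SAP. The shift of 25, 17 or 8 percentage points per participant holds only if the mock-shell column sizes are the real ones, and only if that participant has no other event in the same table row. The conclusion also assumes that treatment-emergent means the On-Treatment state. The appendix titled for treatment-emergent events gives no separate definition of the term, so this is the natural reading.

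This is a defect in a rule, not a missing detail. It should be corrected before unblinding.

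**What to change.** Leave the Pre-Treatment and Post-Treatment rows as they are. Change only the lower bound of the On-Treatment row, in both its words and its formula, to read:

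*AE start date-time ≥ study treatment start date-time where the AE start time is recorded, otherwise AE start date ≥ study treatment start date; and AE start date ≤ study treatment stop date.*

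The stop-date condition has to stay. A row with only a lower bound would make every Post-Treatment event On-Treatment as well, a larger overlap than the one removed. With both bounds, each test onset above takes exactly one state, and untimed Day 1 events are still treated conservatively as On-Treatment.

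Add one sentence stating that 11.3.2, and not the phase table in 11.3.1, governs adverse events, or reconcile the Day 1 boundary in the two tables.

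The cost is a line of SAP text, a clarifying sentence and the matching line in the program that derives the treatment states. No new data are needed, because the Pre-Treatment row already relies on the same event and dosing times.

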5.1. Study Treatment & Sub-group Display Descriptors

| | Treatment Group Descriptions | | | | | | | |
|--|-------------------------------------|----------------------------|---|-----------|--|--|--|--|
| RandAll NG Data Displays for Reporting | | | | | | | | |
| Code | Description | Display Header | Footnote Treatment Description | Order [1] | | | | |
| S1 | CCI15106-IP 60 mg – Single Dose | CCI15106 SD 60mg(HV) | CCI15106-IP 60 mg Single Dose for Part 1, Cohort A | 1 | | | | |
| S2 | CCI15106-IP 120 mg – Single Dose | CCI15106 SD 120mg(HV) | CCI15106-IP 120 mg Single Dose for Part 1, Cohort A | 2 | | | | |
| R1 | CCI15106-IP 30 mg - BID | CCI15106 BID 30mg(HV) | CCI15106-IP 30 mg BID for Part 1, Cohort A | 3 | | | | |
| R2 | CCI15106-IP 60 mg - BID | CCI15106 BID 60mg(HV) | CCI15106-IP 60 mg BID For Part 1, Cohort B | 4 | | | | |
| Р | Placebo | Placebo(HV) | Placebo for Part 1 Cohorts A and B | 5 | | | | |
| S1 | CCI15106-IP 60 mg – Single Dose | CCI15106 SD 60mg(COPD) | CCI15106-IP 60 mg Single Dose for Part 2, Cohort A COPD | 6 | | | | |
| R2 | CCI15106-IP 60 mg - BID | CCI15106 BID 60mg(COPD) | CCI15106-IP 60 mg BID for Part 2, Cohort B COPD | 7 | | | | |
| Р | Placebo | Placebo(COPD) | Placebo for Single Dose and BID for COPD | 8 | | | | |
| BYS | Bystander Cohort | Bystander | Bystander | 9 | | | | |

NOTES:

1. Order represents treatments being presented in TFL, as appropriate.

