11.2. Appendix 2: Schedule of Activities

11.2.1. Protocol Defined Schedule of Events

Screening and follow-up procedures for all cohorts

| Procedure | Screening, ≤ 30 days before D1 for Part 1 or ≤ 45 days before D1 for Part 21 | Follow up 30±2 days after the last dosing day | Notes |
|---|--|---|--|
| Informed consent | Х | | Screening assessments can be performed over multiple screening visits |
| Inclusion and exclusion criteria | X | | If test otherwise performed within 3 months prior to first dose of study treatment, testing |
| Demography | X | | at screening is not required |
| Full physical examination including height and weight, oral examination | Х | | To be drawn fasting (for at least 8 h) To be administered to participants with COPD only, 15-30 minutes prior to spirometry |
| Brief physical examination, oral examination | | Х | To be done at screening for participants with COPD only, following salbutamol dosing To be performed in the bronchoalveolar lavage (BAL) cohorts only to confirm participant |
| Medical history (includes substance usage and Family history of premature CV disease) | х | | eligibility 7. To be performed in the BAL cohorts only to confirm participant eligibility. Can be done pre-dose on Day -1 instead, if required |
| Substance testing (drugs, alcohol) | X | | |
| Assessment of child-bearing potential for females | Х | | |
| Serum pregnancy test in women | X | X | |
| Human immunodeficiency virus (HIV), Hepatitis B (Hep B) and Hepatitis C (Hep C) screen ² | Х | | |
| Haematology, clinical chemistry and urinalysis (include liver chemistries) ³ | Х | X | |
| Salbutamol administration ⁴ | X | | |
| Spirometry ⁵ | X | | |
| 12-lead ECG and vital signs | Х | X | |
| Coagulation parameters ⁶ | X | | |
| Capillary pCO ₂ ⁷ | X | | |
| PK blood sample | | X | |
| AE review | | X | |
| SAE review | X | X | |
| Concomitant medication review | X | X | |

Schedule for Cohort A Part 1

| Procedure | | | | | | | | | | Tre | eatmer | nt Peri | od, Da | ıys | | | | | | | | | |
|---|----|------------------|-----------------|------------|---|---|----|----|-----------------------|----------------|----------------|----------------|--------|-----|----------------|----------------|----|----|----------------|----|----|--------------|----|
| | -1 | 11 | 2 | 31 | 4 | 5 | 6 | 7 | 8 | 9 | 10 | 11 | 12 | 13 | 14 | 15 | 16 | 17 | 18 | 19 | 20 | 21 | 22 |
| Inclusion and exclusion criteria | Х | | | | | | | | | | | | | | | | | | | | | | |

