11.6.2.1. Handling of Missing and Partial Dates

| Element | Reporting Detail |
|---|--|
| General | Partial dates will be displayed as captured in subject listing displays. |
| Adverse Events | The eCRF allows for the possibility of partial dates (i.e., only month and year) to be recorded for AE start and end dates; that is, the day of the month may be missing. In such a case, the following conventions will be applied for calculating the time to onset and the duration of the event: Missing Start Day: First of the month will be used unless this is before the start date of study treatment; in this case the study treatment start date will be used and hence the event is considered On-treatment as per Appendix 3: Study Phases and Treatment Emergent Adverse Events. Missing Stop Day: Last day of the month will be used, unless this is after the stop date of study treatment; in this case the study treatment stop date will be used. Completely missing start or end dates will remain missing, with no imputation applied. Consequently, time to onset and duration of such events will be missing. |
| Concomitant Medications/ Medical History | Partial dates for any concomitant medications recorded in the CRF will be imputed using the following convention: If the partial date is a start date, a '01' will be used for the day and 'Jan' will be used for the month If the partial date is a stop date, a '28/29/30/31' will be used for the day (dependent on the month and year) and 'Dec' will be used for the month. The recorded partial date will be displayed in listings. |

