11.10.5. Safety Tables

| Safety: | Safety: Tables | | | | | |
|---------|---|-------------------------|---|--|---------------------------|--|
| No. | Population | IDSL / Example Shell | Title | Programming Notes | Deliverable [Priority] | |
| Advers | e Events (AEs) | | | | | |
| 3.1. | Safety | AE1 | Summary of Treatment Emergent Adverse Events by System Organ Class and Preferred Term – Part 1 | The general layout of all the safety tables would follow mock shell SAFE_T4 for the column headers and order for both Part 1 and Part 2 tables. This will not include Cohort C, Part 1. | SAC | |
| 3.2. | Safety | AE1 | Summary of Treatment Emergent Adverse Events by System Organ Class and Preferred Term – Part 2 | | SAC | |
| 3.3. | Bystander Safety (Part 1, Cohort C) | AE1 | Summary of Treatment Emergent Adverse Events by System Organ Class and Preferred Term – Bystander | | SAC | |
| 3.4. | Safety | AE1 | Summary of Treatment Related Adverse Events by System Organ Class and Preferred Term – Part 1 | This will not include Cohort C, Part 1. | SAC | |
| 3.5. | Safety | AE1 | Summary of Treatment Related Adverse Events by System Organ Class and Preferred Term – Part 2 | | SAC | |
| 3.6. | Bystander Safety (Part 1, Cohort C) | AE1 | Summary of Treatment Related Adverse Events by System Organ Class and Preferred Term – Bystander | | SAC | |
| 3.7. | Safety | AE5A | Summary of Treatment Emergent Adverse Events by System Organ Class and Maximum Severity – Part 1 | This will not include Cohort C, Part 1. | SAC | |
| 3.8. | Safety | AE5A | Summary of Treatment Emergent Adverse Events by System Organ Class and Maximum Severity – Part 2 | | SAC | |

| Safety: | Safety: Tables | | | | | |
|---------|---|-------------------------|---|---|---------------------------|--|
| No. | Population | IDSL / Example Shell | Title | Programming Notes | Deliverable [Priority] | |
| 3.9. | Bystander Safety (Part 1, Cohort C) | AE5A | Summary of Treatment Emergent Adverse Events by System Organ Class and Maximum Severity – Bystander | | SAC | |
| 3.10. | Safety | AE5A | Summary of Treatment Related Adverse Events by System Organ Class and Maximum Severity – Part 1 | This will not include Cohort C, Part 1. | SAC | |
| 3.11. | Safety | AE5A | Summary of Treatment Related Adverse Events by System Organ Class and Maximum Severity – Part 2 | | SAC | |

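### Treatment-emergent is never defined, and its only candidate, the On-Treatment state, ends on the calendar date of the last dose

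*SAP*

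**What the plan says.** SAP section 7.2 sends the reader to Appendix 3 for AE treatment states. It then speaks of treatment emergence only to say that an event whose emergence cannot be assessed counts as emergent. Appendix 3 carries treatment-emergent AEs in its title, but section 11.3.2 defines only three states:

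- Pre-Treatment is onset before the first dose.
- On-Treatment is given in words, "If AE onset date is on or after treatment start date & on or before treatment stop date", and as a formula, "Study Treatment Start Date ≤ AE Start Date ≤ Study Treatment Stop Date".
- Post-Treatment is "AE Start Date > Study Treatment Stop Date".

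A note adds: "If the study treatment stop date is missing then the AE will be considered to be On-Treatment".

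Section 7.2 lists tabulations of all AEs by dose. The matching displays in section 11.10.5 are titled "Summary of Treatment Emergent Adverse Events by System Organ Class and Preferred Term" (Tables 3.1–3.3), with the severity versions in Tables 3.7–3.9. The schedule in section 11.2.1 includes AE review at a follow-up visit "30±2 days after the last dosing day".

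For partial AE end dates, section 11.6.2.1 says: "Missing Stop Day: Last day of the month will be used, unless this is after the stop date of study treatment". In that case the treatment stop date is used instead.

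**The concern.** A programmer building the treatment-emergent tables has one route through the text: take Appendix 3, keep On-Treatment events, and drop Pre- and Post-Treatment ones. The calendar date of the last dose is then the last day on which an event can be counted. In a cohort that receives one dose, start and stop dates coincide, and an event the next morning falls outside the window.

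AEs are a primary endpoint and no hypothesis is tested, so the descriptive tables by dose carry the safety conclusion. Section 5.1 also pools Part 2 placebo across the single-dose and BID cohorts. On this reading that column would mix 1-day and 14-day windows.

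Two related gaps follow. Part 1 Cohort A takes three treatments in turn, and the plan does not say how an event between doses reaches a dose column. The end-date imputation assumes that no AE outlasts or follows treatment, although AEs are collected for about a month after the last dose.

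**Working it through.** The SAP states no figure to reproduce; this is a classification rule applied to the schedules in section 11.2.1.

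**Inputs**

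- Part 2 Cohort A: one dose, Day 1 (section 5.1: "CCI15106-IP 60 mg Single Dose for Part 2, Cohort A COPD").
- Cohorts B, Parts 1 and 2: BID dosing, Days 1–14.
- Part 1 Cohort A: 60 mg on Day 1, 120 mg on Day 3, 30 mg BID on Days 6–19.
- Follow-up: 30 days after the last dosing day, range 28 to 32.

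**On-Treatment days**

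On-Treatment days = stop − start + 1. Days to follow-up = stop − start + 1 + 30.

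| Cohort and dates used | On-Treatment | Days to follow-up (range) | Fraction (range) |
|---|---|---|---|
| Part 2 A | 1 − 1 + 1 = 1 | 31 (29–33) | 3.2% (3.4–3.0%) |
| Cohorts B | 14 − 1 + 1 = 14 | 44 (42–46) | 31.8% (33.3–30.4%) |
| Part 1 A, study-level dates | 19 − 1 + 1 = 19 | 49 (47–51) | 38.8% (40.4–37.3%) |

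**Part 1 Cohort A between doses**

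- Dates per treatment: 60 mg is On-Treatment on Day 1 only, 120 mg on Day 3 only, and 30 mg BID on Days 6–19. Days 2, 4 and 5 are Post-Treatment to the preceding dose.
- Study-level dates: Days 2, 4 and 5 lie within Days 1–19 and are On-Treatment. No rule says whether they enter the 60 mg, 120 mg or 30 mg BID column.

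Section 11.3.2 does not say which dates apply. The exposure shell (SAFE_T5) works by period, but nothing carries that over to AEs. Either way the AE tables by dose lack a needed rule.

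**Partial end date**

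Section 11.3.2 gives duration = resolution date − onset date + 1. Take an AE that starts k days after the treatment stop date and has no end day. Its end month cannot precede its onset month, so the month end falls after treatment stop and the reset always applies.

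Duration = stop − (stop + k) + 1 = 1 − k.

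The imputed end precedes onset for every k ≥ 1. Duration is 0 at k = 1 and negative from k = 2. With dose and stop on Day 1 and onset on Day 3, it is 1 − 3 + 1 = −1 day.

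**Bystanders**

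Table 3.3 reports treatment-emergent AEs for Part 1 Cohort C, whose members are exposed rather than dosed. Appendix 3 defines no start or stop date for them.

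**The case against.** The SAP nowhere says that treatment-emergent means On-Treatment, or that Post-Treatment events are left out. Section 7.2 speaks of all AEs and treats undeterminable cases as emergent, so a reading of emergent as simply not Pre-Treatment also fits the text. This stands: the loss of events is conditional on the more natural reading. It does not remove the defect, because a plan that allows both readings leaves the content of its main AE tables to the programmer.

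A reader might infer that every AE from Day 2 is lost after any single dose. The documents support that only for Part 2 Cohort A. In Part 1 Cohort A, study-level dates make Days 2, 4 and 5 On-Treatment. Even in Part 2 Cohort A, events with a missing treatment stop date, or with a partial start date imputed to the start of treatment, still count.

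A reader might also infer that the single-dose columns are shown to look safer than the BID columns. They are not. The fractions are calendar time, the SAP gives no AE timing, and on the same reading the Cohorts B lose 30 of their 44 days.

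The related, serious and discontinuation tables (3.4–3.6, 3.10–3.18) and the all-AE listings (29–31) are not titled as treatment-emergent, so late events may still appear there. The end-date error affects only calculated durations: listings show dates as captured, and no planned table is titled as AE duration.

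**Conclusion.** The concern holds in conditional form. Treatment-emergent is undefined, and the only window offered closes on the date of the last dose. If that window is used, Tables 3.1–3.3 and 3.7–3.9 omit all fully dated AEs after Day 1 in Part 2 Cohort A and after Day 14 in the Cohorts B. This rests on dosing as scheduled and on known treatment stop dates.

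Two parts do not depend on that reading. AEs between doses in Part 1 Cohort A have no stated attribution rule. The partial end-date rule gives impossible durations for any AE starting after the last dose. How many events are affected cannot be derived from the document.

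**What to change.** Add to Appendix 3, before unblinding:

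1. **Definition.** Treatment-emergent means onset at or after the first dose, by date and time where available, through the follow-up visit. For Part 1 Cohort C, use first exposure. Make section 7.2 and the table titles agree with it.
2. **Attribution in Part 1 Cohort A.** Assign each AE to the most recently started treatment: 60 mg until the 120 mg dose, 120 mg until the first 30 mg BID dose, and 30 mg BID thereafter through follow-up. The windows are then about 2 days (Days 1–2), 3 days (Days 3–5) and 44 days (Days 6–49). Footnote these lengths on each AE table. The 30 mg BID to 60 mg ratio becomes 44:2, or 22:1, against 14:1 under per-treatment dates in the current rule, so the columns remain unequal in observation time.
3. **Partial end date.** In section 11.6.2.1, impute the earlier of month end and study end date, never before onset.

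Follow-up is one possible cut-off. It is proposed because the schedule already collects AEs to that point; the SAP gives no residual-effect period to support a shorter one.

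The cost is SAP wording and a change to the AE derivation, with no new data. The downside is that some later, unrelated events will enter the tables.
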